The parents or legal guardians of the participants will complete a structured questionnaire at the baseline and after the last session. Demographic information, including age, gender, Medication, ADHD symptoms and game experience will be recorded at the baseline. The questionnaires include questions about social skills and executive functioning. The satisfaction of the participants and their parents or legal guardians towards the training program will be assessed at week 3. The VR sickness of the participant will be evaluated after each session. The assessor will be blind to the treatment condition. The questionnaires will include the following scales:

Primary outcome measure

1. Process evaluation

The process evaluation of the training will be assessed by investigating: (i) training acceptability as measured by the participants' attendance and compliance; (ii) recruitment rate; (iii) participant completion.

(i) Assessment of training acceptability and compliance

The attendance of the participants during the trainings will be recorded. To verify the validity of the findings, training non-adherence of the participants will be terminated which will be stated in the consent form. The absence of any training session will be considered as non-adherence. The participants will be asked about their willingness of partaking in this kind of training by one 7-point Likert scale question which is used to reflect the acceptability to the intervention. The retention rate should be at least 85% according to the feasibility RCT.

The compliance with the training program will be evaluated by the communication log which the parents record their children's daily activity and emotion in the 3-week intervention period. The participants' parents will be reminded to attend the training through telephone in the first four training sessions and WhatsApp or WeChat in the fifth and eighth training sessions. No reminder follow-up will be made in the remaining four sessions. These data will be used to evaluate their compliance.

(ii) Recruitment rate

The recruitment rate is at least 48.5% of all referrals according to the feasibility study.

(iii) Participant completion

Participants attending at least nine (i.e., 75%) of the 12 sessions are considered to have completed the program.

Secondary outcome measure

1. Social Skills Rating Scale (SSRS-P)

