All statistical analyses will be performed in SPSS version 26.0 software (IBM Corp, Armonk, NY, USA) and are two-sided with a level of significance of < 0.05 . Demographic information of the participants will be summarised with frequency and percentage for categorical variables. The continuous variables will be summarised by mean and standard deviation. The change between baseline and week 3 within each arm will be tested using t-tests. To examine the between-group difference in terms of measure outcomes from baseline to week 3, repeated analyses of covariance (ANCOVA) with adjustment of baseline characteristics will be conducted. To evaluate the improvement during the intervention period among the three groups, f-tests will be performed on primary and secondary outcome measures at the beginning of the first session and at the end of the last session. An intention-to-treat analysis will be performed. This analysis is regarded as the most appropriate approach to analyse RCT data by the highest-quality journals, which have utilised the CONSORT standard.

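### The first-session/last-session F-test across three groups cannot be run on the primary process outcomes, and the absence rule sits uneasily with the 9-of-12 completion rule

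*Combined protocol and SAP*

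**What the plan says.** The Statistical analysis plan names three procedures for outcomes.

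- Within arms: "The change between baseline and week 3 within each arm will be tested using t-tests".
- Between groups: a repeated ANCOVA from baseline to week 3, adjusted for baseline characteristics.
- For improvement, comparing all of the arms: "f-tests will be performed on primary and secondary outcome measures at the beginning of the first session and at the end of the last session".

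The Primary outcome measure section lists one primary outcome, a process evaluation with three components.

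- **(i) Acceptability and compliance.** "The attendance of the participants during the trainings will be recorded". There is also a 7-point willingness item and a communication log kept by parents. A benchmark is given: "The retention rate should be at least 85% according to the feasibility RCT". On absence, the section states "The absence of any training session will be considered as non-adherence", and that "training non-adherence of the participants will be terminated which will be stated in the consent form".
- **(ii) Recruitment rate.** "The recruitment rate is at least 48.5% of all referrals according to the feasibility study".
- **(iii) Completion.** "Participants attending at least nine (i.e., 75%) of the 12 sessions are considered to have completed the program".

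The Waitlist control group section gives that arm no training during the 3-week period. Under Sample size, 90 children are planned, 30 per arm, with 15% attrition expected.

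**The concern.** The F-test sentence suits scores taken before the first and after the last session, as the SSRS-P and BRIEF are. But it names the primary outcomes explicitly, and those have a different structure. If the named test cannot be run on the trial's only primary outcome, whatever is eventually reported for that outcome will not be the planned analysis, and the choice of replacement will be made after the data are in hand.

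The second problem concerns how completion is counted. One rule tolerates no absence and the other tolerates three. Unless the text says how they work together, the same attendance records can give different completion rates.

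A smaller gap is that the 85% retention figure has no stated denominator, while the protocol's own expected attrition of 15% puts expected retention exactly on that mark.

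**Working it through.** **1. Does each outcome have the structure the tests need?** The F-test needs a value in each of three groups at two times. The t-test and the ANCOVA need a baseline and a week-3 value.

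| Outcome | Value at both times? | Exists in the waitlist arm? | Named tests fit? |
|---|---|---|---|
| Recruitment rate | No; one proportion of referrals | No arm dimension | No |
| Attendance | No; accumulates over 12 sessions | No | No |
| Completion | No; known only at the end | No | No |
| Willingness item | No baseline score described | Asks about the training | No |
| Communication log | No; daily over 3 weeks | As a training-compliance measure, no | No |
| Satisfaction | Week 3 only | Asks about the training | No |
| SSQ | After each session | No VR sessions | No |
| SSRS-P, BRIEF | Yes | Yes | Yes |
| Psychiatrist's rating | Timing not stated | Not stated | Only if scored at both times |

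The only descriptive sentence using frequencies and percentages in the analysis section is written for demographic information.

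**2. The plan's own figures.** 9/12 = 75% and 3 × 30 = 90, as stated.

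**3. The two attendance rules read together.** Suppose a child stops at the first absence. A child whose first absence is session k has attended k − 1 sessions. For k ≤ 9 that is at most eight, so the child cannot complete. For k = 10, 11 or 12 it is nine, ten or eleven, so the child is both terminated and a completer.

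**4. Size of the difference.** Let a be the chance of attending any one session. The documents give no value, so 0.90 to 0.98 is assumed. With independent sessions:

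- termination at first absence: P(complete) = a⁹, since the first nine must all be attended;
- no termination: P(complete) = P(Bin(12, a) ≥ 9).

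| a | With termination | Without |
|---|---|---|
| 0.90 | 38.7% | 97.4% |
| 0.95 | 63.0% | 99.8% |
| 0.98 | 83.4% | 99.99% |

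Absences probably cluster within children. A beta-binomial model with mean 0.95 and an assumed within-child correlation gives:

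| Correlation | With termination | Without | Gap |
|---|---|---|---|
| 0 | 63% | 99.8% | 37 points |
| 0.1 | 72% | 97% | 25 points |
| 0.3 | 81% | 94% | 13 points |

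**5. Retention denominator.** The smallest counts that reach 85%, with exact (Clopper-Pearson) 95% intervals:

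- all 90: 77/90 = 85.6% (76.6% to 92.1%), at most 13 losses;
- the 60 trained: 51/60 = 85.0% (73.4% to 92.9%), at most 9 losses;
- one arm: 26/30 = 86.7% (69.3% to 96.2%), at most 4 losses.

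Two illustrative loss patterns near 15% overall:

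- 10 trained and 3 waitlist children lost: 50/60 = 83.3% (misses), 77/90 = 85.6% (meets);
- 6 trained and 8 waitlist children lost: 54/60 = 90.0% (meets), 76/90 = 84.4% (misses).

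**The case against.** The best defence is that the F-test sentence is loosely drafted. Its stated purpose is to evaluate improvement; a recruitment rate cannot improve, so a sensible analyst would apply it to scored measures and report the rest descriptively. That is probably what would happen, but the sentence names the primary outcomes, and the section offers no other method for them.

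Three stronger readings are tempting, and the documents do not support them.

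- **That the primary outcome has no benchmark.** The protocol states 85% for retention and 48.5% for recruitment, and descriptive reporting beside those figures is legitimate. Retention itself is not one of the three listed components. Its figure sits under training acceptability, which leans towards the trained arms, so the missing denominator alone would be only a missing detail.
- **That the two attendance rules are logically incompatible.** They are not: step 3 applies both at once. Non-adherence and completion can be separate labels, and the termination sentence is garbled and does not say that stopping is immediate. The supportable statement is that the rules are in tension and their joint operation is unclear.
- **That the completion gap is 37 points.** That figure depends on independent sessions. Clustering of absences shrinks it considerably, as step 4 shows.

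Nor does the denominator choice favour one verdict: the two loss patterns flip in opposite directions.

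**Conclusion.** The analysis is wrong as written for the primary process outcomes. This rests on the structure of the outcomes and on no numerical assumption, and confidence in it is high. The same mismatch reaches the willingness item, communication log, satisfaction and SSQ.

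The tension between the absence and completion rules is also real, though its size is uncertain. At an assumed 95% attendance, the difference in completion runs from about 13 points (correlation 0.3) to 37 points (independence). Both the attendance rate and the correlation are assumptions, so these are illustrations and not forecasts. The retention denominator is a minor addition.

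A reader might infer that the sample size or the error rate is compromised. Neither is affected. The point should be fixed, and a wording change is enough.

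**What to change.** In the Statistical analysis plan:

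- Restrict the t-test, F-test and ANCOVA sentences to outcomes scored at both baseline and week 3: SSRS-P, BRIEF, and the psychiatrist's rating only if it is scored at both times.
- Report recruitment and retention as proportions with exact 95% confidence intervals beside the stated 48.5% and 85%, kept as point benchmarks.
- Report attendance, completion, and the training-related acceptability, compliance and satisfaction measures in the two training arms only, and SSQ in the VR arm, as descriptive summaries with confidence intervals.
- Name the retention denominator in advance: all 90, the 60 trained, or per arm.

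In the Primary outcome measure section, reconcile the absence and termination wording with the 9-of-12 completion definition before completion is computed. Which rule should apply is for the investigators; this review takes no position.

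The cost is rewording, with no new data, visits or participants. One small downside is that feasibility results will carry visibly wide intervals: completion of 27/30 in one arm (90%) has an exact 95% interval of 73% to 98%.

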The study targets children with diagnosed ADHD and aims to (1) develop a social virtual reality-based intervention, (2) investigate its effects on improving the social skills and executive functioning of inhibitions, emotional control and attention of the children compared to traditional social skills training and (3) evaluate the subjects acceptability and compliance with social VR training for enhancing social interaction skills. It is hypothesised that the social interaction skills of the participants in the social VR training group are likely to perform better than those in the traditional social skills training group. Participants in the waitlist control group will receive no change in social interaction skills compared with the two intervention groups.

Methods/ Design

The study will be a three-arm randomised controlled trial comparing the effects of a social VR-based intervention with traditional social skills training on social skills and executive functioning of children with ADHD. Participants in the social VR intervention group and traditional social skill training group will receive 12 training sessions for 3 weeks (4 sessions per week), and participants in the waitlist control group will be asked to retain their usual lifestyles for 3 weeks. The overall design of the study is illustrated in Figure 1. Ethical

approval for the study has been obtained by the Human Subjects Ethics Application Review Committee of The Hong Kong Polytechnic University.

[figure not shown]

Figure 1. Study design

Participants

Individuals who meet the inclusion criteria will be recruited. The criteria are as follows: 1) aged between 6 and 12 years; 2) ethnic Chinese; 3) residing in Hong Kong; 4) having received a diagnosis of ADHD by Child Assessment Service in Hong Kong or via private practice; 5) stable on pharmacological and/or psychological treatment for ADHD 8 weeks before baseline (determined by health care professionals on the basis of medication data and behavioural observation); 6) no initiation or change of pharmacological treatment for ADHD during the intervention period; 7) ability to read Chinese, and speak and listen to Cantonese by the child and by at least one of their parents or legal guardian; 8) willing to provide informed consent by both participants and one of their parents or legal guardian.

Exclusion criteria are as follows: 1) comorbid autism; 2) mental retardation; 3) an estimated

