Social VR intervention is developed to enhance the social interaction skills of children. The participants will wear a head-mounted display (HMD) for the Social VR intervention. Each session of the Social VR intervention lasts for a maximum of 20 minutes to ensure the participants focus on the intervention and prevent causing any physical effect. The duration will be adjusted depending on the emotion of the participants during the intervention. The Social VR intervention will mainly help the participant to enhance their social interaction skills and executive function. The intervention contains three real-life virtual scenarios, including (1) classroom and playground, (2) MTR station and compartment, and (3) street and building. One scenario will be adopted in each session. The sequences of the scenarios used in each session will be the same for all participants. During the Social VR intervention, one RA will also appear as one avatar in the scenario to guide the participants to complete a series of tasks. Each intervention session will be conducted in a classroom independently for each participant.

Traditional social skills training

An experienced SEN teacher will teach the participants social interaction skills through tradidactic instructions and role-play activities. Four modules will be covered in the 3-week training: (1) how to introduce yourself and basic social skills; (2) how to listen to others; (3) how to share with others; (4) learn to know how people feel and how to empathise. These modules have been applied in many studies. The content of this training will be as similar as possible to the Social VR training. The training lasts 20 minutes which depends on the emotion of the participants. Each training session will be conducted in a classroom independently for each participant.

Waitlist control group

The participants in this group will receive no training and they can participate in the social VR training after the intervention period. To ensure consistency of the experiment, the participants are not allowed to initiate or change their pharmacological treatment during the 3-week intervention period.

Measures

Questionnaires

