The social skills of the children will be assessed by Chinese-translated SSRS-P which will be scored by the participants' parents before the first session and after the last session. This scale consists of 3 subscales, including self-control, assertiveness and initiative and cooperation, with a total of 31 items. A 3-point Likert scale (never, sometimes, often) is used to score. The SSRS-P is a validated instrument that has been commonly adopted in clinical trials of psychiatric and neurological disorders.

2. Child psychologist's assessment

One child psychiatrist will score the performance of the participants in the 5-minute tasks to obtain an objective evaluation. Broken blinding is unavoidable in child psychiatrist's assessment. To minimise unblinding bias during the assessment, each participant will be identified by a case number.

3. Behaviour Rating Inventory of Executive Function (BRIEF)

Chinese-translated BRIEF used to assess the executive functioning of children which will be scored by the participants' parents before the first session and after the last session. The subscales of inhibitions (16-item) and emotional control (10-item) will be adopted in this study. A 3-point Likert scale (never, sometimes, often) is used to score.

4. Satisfaction

Satisfaction is measured by a 7-point Likert scale, 'What grade would you give to this training program?'. Both participants and parents/ guardians have to answer.

5. Simulator Sickness Questionnaire (SSQ)

The SSQ measures motion sickness or physical discomfort of participants in VR environment. Nine items will be measured, including discomfort, fatigue, headache, eyestrain, sweating, nausea, difficulty concentrating, blurred vision and dizziness, with yes or no questions for each item.

6. Assessment of safety

a) Adverse events

RA1 will ask participants' parents/ guardians, using open-ended questions, whether the participants experienced any adverse events during training. The severity and relationship of the adverse event to the intervention will be documented and investigated.

b) Reasons for withdrawal

When a subject withdraws before completing the study, the reasons for withdrawal will be recorded.

Statistical analysis plan

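### The post-treatment time point is given both as the last session and as week 3; the session anchor cannot be applied to the waitlist and is ambiguous for children who stop early

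*Combined protocol and SAP*

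**What the plan says.** Collection of the parent-rated scales is tied to sessions. Under Questionnaires, parents or guardians "will complete a structured questionnaire at the baseline and after the last session". Under Secondary outcome measure, items 1 (SSRS-P) and 3 (BRIEF), each scale is "scored by the participants' parents before the first session and after the last session". The Statistical analysis plan uses the same anchors for the three-group F-tests, on values "at the beginning of the first session and at the end of the last session".

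Other sentences use the calendar. In the Statistical analysis plan, "The change between baseline and week 3 within each arm will be tested using t-tests", and the between-group ANCOVA covers the same interval. Under Questionnaires, satisfaction is placed at week 3.

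Under Methods/ Design, the two active arms have 12 sessions in 3 weeks, 4 per week, while "participants in the waitlist control group will be asked to retain their usual lifestyles for 3 weeks". The Waitlist control group section adds: "The participants in this group will receive no training and they can participate in the social VR training after the intervention period".

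Three further statements bear on children who stop. Under Process evaluation, absence from any session is non-adherence and leads to termination, yet attending 9 of 12 sessions counts as completion. The Statistical analysis plan promises an intention-to-treat analysis.

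**The concern.** A three-arm comparison of change needs the same post-treatment time in every arm, fixed independently of how much training a child received. Here the instruction that produces the SSRS-P and BRIEF values depends on training sessions, and the waitlist has none during the comparison period. Two of the three planned analyses call for a week-3 value, but no collection instruction for these scales schedules one.

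Within the active arms, a session anchor lets attendance decide when, or whether, a child is scored. If children who do poorly are the ones who stop, their scores come earlier than those of the rest of their arm or are lost, and the comparison no longer covers everyone randomised at a common time. SSRS-P and BRIEF are the parent-rated measures behind the stated aims on social skills and executive functioning, so the point matters even though they are secondary outcomes.

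**Working it through.** **1. The plan's schedule reproduces.** 3 weeks × 4 sessions per week = 12 sessions, and 9/12 = 75%, both as stated. Session 12 falls at week 3, so the two anchors coincide for a child who attends throughout.

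**2. Waitlist.** Sessions between baseline and week 3: 0. Children concerned: 30 of 90, one third of the sample. The phrase "before the first session and after the last session" has no referent for them in the trial period, and neither do the F-test anchors. For the parent questionnaire only the second time point fails, because its first is simply baseline. The within-arm t-test sentence covers every arm, so it implies a week-3 value for the waitlist, but the collection text does not schedule it.

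**3. Early stoppers, if the last session means the last one attended.** Assume even spacing, so session k falls at k/4 weeks and the assessment precedes week 3 by 3 − k/4 weeks.

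| Last session attended | Time (weeks) | Early by (weeks) |
|---|---|---|
| 12 | 3.00 | 0 |
| 9 | 2.25 | 0.75 |
| 8 | 2.00 | 1.00 |
| 4 | 1.00 | 2.00 |
| 1 | 0.25 | 2.75 |

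**4. How many children.** The Sample size section expects 15% attrition: 0.15 × 30 = 4.5 per arm. If all of these in an active arm stopped after session 9, that arm's mean assessment time would be 0.85 × 3 + 0.15 × 2.25 = 2.89 weeks. If all stopped after session 1, it would be 0.85 × 3 + 0.15 × 0.25 = 2.59 weeks. The stopping times are an assumed range, not figures from the plan.

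**5. Early stoppers, if the last session means scheduled session 12.** A child who was terminated or withdrew does not reach it, and no sentence says that an assessment is still sought. The same 15% would leave 0.85 × 30 = 25.5 scored children per arm, with the rest missing.

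**6. Bias.** Converting these timing gaps or missing values into a bias needs the course of the scores over the 3 weeks and the reasons for stopping. The documents give neither.

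**The case against.** The strongest reply is that the plan already has a common calendar point. The t-tests and the between-group ANCOVA both run to week 3, and the waitlist has the same 3-week period, so the session wording is loose drafting for the same moment. Most of this stands. It would be wrong to infer that outcomes are timed to the last session instead of week 3, or that the waitlist has no valid assessment point. Week 3 is implied for it. What remains is that the collection rule and the F-tests state something else, which cannot be carried out in one arm.

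A reader might also infer that waitlist children are scored after their own VR course, at about week 6 (3 weeks waiting plus 3 weeks of VR), so that the control is already treated. The documents do not support this. The F-test sentence is confined to improvement in the intervention period, and VR is offered to the waitlist only after it. Still, no sentence says that the waitlist assessment must come before VR begins.

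A third tempting reading is that 4 to 5 children per active arm will be scored early. No sentence says so. In a fixed 12-session course the last session may well mean session 12, and attrition usually means no value at all. Given the termination rule, missing values are at least as likely as early ones.

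Finally, Figure 1 (study design) is not shown in the available text and might give assessment points by arm. The primary outcomes are process measures that do not depend on this timing. Both points limit the concern, but neither removes the conflict in the written instructions.

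**Conclusion.** The concern holds as an inconsistency between two anchors, with consequences for the secondary efficacy comparisons. The session anchor cannot be applied to 30 of 90 children. For those who stop early it is ambiguous: they are scored up to 2.75 weeks before week 3 or not scored, and either conflicts with an intention-to-treat analysis at a common time. The 4 to 5 children per active arm is an illustration from the plan's own attrition figure. The timing gaps rest on even spacing and on reading the last session as the last attended. No bias estimate can be given. This is more than missing detail, because a stated collection and analysis rule fails in one of three arms, and it should be corrected.

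**What to change.** - In Questionnaires, in Secondary outcome measure items 1 and 3, and in the F-test sentence of the Statistical analysis plan, replace the session anchors with one calendar assessment. Set it at week 3 from the first scheduled session in the active arms and 3 weeks from baseline in the waitlist, with a short common window and regardless of sessions attended.
- State that the waitlist assessment is completed before any VR session is offered to that child.
- State that the week-3 parent questionnaire is sought from families whose child stopped or was terminated from training.
- Use the same week-3 values in the t-tests, ANCOVA and F-tests.
- Reconcile the two Process evaluation statements, that any absence leads to termination and that 9 of 12 sessions is completion. Say whether termination ends training only or assessment as well.

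The cost is a few short text edits and a few more contacts with families who stopped training. Parent questionnaires need no session. The sample size, significance level and choice of analyses do not change.

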IQ lower than 85 (using the Wechsler Intelligence Scale for Children – Fourth Edition (Hong Kong) (WISC-IV(HK))); 4) autism spectrum disorder (previously diagnosed by health care professionals), 5) comorbid acute psychiatric disorder (previously diagnosed by health care professionals); and 6) with a severe physical disability (e.g., blindness, deafness) or learning disability (e.g., dyslexia).

Sample size

The guidelines of Whitehead et al. (2016) suggested that recommended that at least 16 subjects per group for medium effect size in pilot RCT and 15% attrition over time can be expected. A total of 90 participants will be recruited which fulfils the minimum number suggested by Whitehead et al. (2016). 30 participants in the social VR group, 30 in the traditional social skills group and 30 in the waitlist control group. This sample size is comparable to those used in the published pilot study on children with ADHD. For instance, van der Oord et al. (2014) recruited 40 participants (20 in the control group and 20 in the interventional group) to examine the efficacy of computerized executive functioning remediation training with game elements in children with ADHD.

Procedure

Recruitment

Participants will be recruited from six primary schools and community centres. Interested participants or parents who provide written informed consent will be further evaluated for inclusion and exclusion criteria by a trained research assistant. Participants who meet the inclusion criteria in the study will be invited to perform an IQ test at the university at baseline.

Randomisation

Eligible participants will be randomized to the social VR (Social VR) group, traditional social skills training group or waitlist control group. A computer-generator randomiser will be used to generate the random allocation list. The randomisation will be undertaken by another research assistant not directly involved in the study. A number generated by the computer will be assigned to each eligible subject who will be randomly allocated to the three different groups by using the number. The participants and their parents or legal guardians will be blind to the assignment process. Parents or legal guardians will receive an email and a telephone call with notification to Group 1, Group 2 or Group 3.

Social VR Intervention

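### Intention-to-treat is promised, but no rule covers missing week-3 scores, so by default the trained-versus-waitlist comparisons of SSRS-P and BRIEF are complete-case with possibly unequal loss

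*Combined protocol and SAP*

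**What the plan says.** The Statistical analysis plan gives the analysis population in one sentence, "An intention-to-treat analysis will be performed", followed by an appeal to CONSORT practice. It does not define the analysis set, and it gives no rule for missing scores and no sensitivity analysis. It names three methods:

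- Within arms: "The change between baseline and week 3 within each arm will be tested using t-tests".
- Between arms: "repeated analyses of covariance (ANCOVA) with adjustment of baseline characteristics will be conducted".
- Across all arms together: "f-tests will be performed on primary and secondary outcome measures at the beginning of the first session and at the end of the last session".

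Missing scores are foreseen. The Sample size section says "15% attrition over time can be expected", and the process evaluation sets a retention target of 85%. The same section says "training non-adherence of the participants will be terminated which will be stated in the consent form", and it sets the trigger for this rule: "The absence of any training session will be considered as non-adherence". Yet under Participant completion it counts 9 of 12 sessions as completing the programme.

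Under Secondary outcome measure, parents score the SSRS-P and BRIEF before the first session and after the last one. For withdrawals, only the reasons are recorded. The waitlist arm has no sessions during the three weeks.

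**The concern.** A change score, or an ANCOVA on baseline and week-3 values, cannot use a child with no week-3 value unless one is imputed. The plan does not say that terminated or withdrawn children are still assessed, and the post score is tied to a last session that such a child may never reach. Followed as written, the plan therefore analyses children who finished and reports the result as intention-to-treat.

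The one stated termination rule depends on missing a session, and only the trained arms have sessions. If the children who leave training are those doing badly, the remaining trained children look better against the waitlist even when training does nothing. SSRS-P and BRIEF are secondary outcomes, but they carry the trial's hypotheses about social skills and executive function.

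**Working it through.** **Inputs from the documents.** 30 children per arm, 90 in total; 15% attrition and 85% retention; 12 sessions in each trained arm and none in the waitlist arm; two-sided 5% significance.

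**Step 1: the plan's own figures.** 3 × 30 = 90, and 15% attrition agrees with 85% retention. The minimum of 16 per group, inflated for 15% loss, is 16 / 0.85 = 18.8, so 19 per group and 57 in total; 90 exceeds this. No power figure is given, so there is none to reproduce.

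**Step 2: children without both scores.** 0.15 × 90 = 13.5, so about 13 or 14 children. About 25.5 of 30 per arm remain if loss is even.

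**Step 3: what each method needs.** The change t-test and the repeated ANCOVA need both scores. F-tests run separately at each time point would use whoever has that score: all children at baseline, but only those with a post score at the end.

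**Step 4: where the absence rule can act.** Assume each session is attended with probability p, independently. The share missing none of 12 is p^12.

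- p = 0.99: 0.886, or 26.6 of 30.
- p = 0.98: 0.785, or 23.5 of 30.
- p = 0.95: 0.540, or 16.2 of 30.

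The 85% retention target would need p = 0.85^(1/12) = 0.9865. In the waitlist arm this rule removes no one.

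**Step 5: illustration of bias.** Assume no true effect and normal change scores. A child leaves when a latent score, correlated c with change, falls below the quantile z for the lost fraction q. The remaining children's mean change is then shifted by c × λ(q) SD, with λ(q) = φ(z) / (1 − q).

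- λ(0.20) = 0.280 / 0.80 = 0.350
- λ(0.05) = 0.103 / 0.95 = 0.109
- λ(0.225) = 0.300 / 0.775 = 0.387
- λ(0) = 0

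The bias is c times the difference between arms. Both splits average 15%: (20 + 20 + 5)/3 and (22.5 + 22.5 + 0)/3. Type I error comes from simulation (30 per arm, 40,000 trials, two-sample t-test on completers).

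| Loss, trained vs waitlist | c | Bias (SD of change) | Type I error |
|---|---|---|---|
| 20% vs 5% | 0.2 | 0.2 × 0.241 = 0.05 | about 5.5% |
| 20% vs 5% | 0.5 | 0.5 × 0.241 = 0.12 | about 7% |
| 20% vs 5% | 0.8 | 0.8 × 0.241 = 0.19 | about 12% |
| 22.5% vs 0% | 0.5 | 0.5 × 0.387 = 0.19 | about 10% |
| 22.5% vs 0% | 0.8 | 0.8 × 0.387 = 0.31 | about 20% |
| 15% vs 15% | any | 0 | about 5% |

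**Step 6: what a remedy can achieve.** Suppose baseline and change correlate at −0.4 (assumed). Baseline adjustment, with or without within-arm imputation from baseline, then removes only about 0.4² = 0.16 of the bias. In the worst row about 0.84 × 0.31 = 0.26 SD remains (0.27 in simulation). Giving missing trained children the waitlist's change leaves 0.775 × 0.31 = 0.24 SD. In simulation it lowers type I error from about 20% to 13% in that row, and from about 7% to 5% at 20% versus 5% with c = 0.5.

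**The case against.** Five points stand against a stronger reading.

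- A reader might infer that the plan commits to a completers' analysis. It does not. It is silent on imputation and on assessing children who stop, and a parent-rated scale can be completed without the child attending. Complete-case is the default reading, not a stated one.
- A reader might infer that all three methods need both scores. Separate F-tests at each time point do not.
- A reader might infer that unequal loss is certain. The absence rule can act only in the trained arms, but waitlist children can also be lost: they must not change medication, and their parents must return the questionnaire. The loss splits above are assumptions.
- A reader might infer that the main question, social VR against traditional training, is biased in the same way. Both arms have 12 sessions and the same absence rule. With equal loss and equal selection, the bias in that contrast is nil.
- The figures depend on who leaves. With 17.5%, 17.5% and 10% loss at c = 0.5, the bias is 0.06 SD and type I error about 5%. If children who have improved are the ones who leave, the sign reverses.

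What remains is that the label and the named methods do not match once a week-3 score is missing, and the plan expects such scores to be missing.

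**Conclusion.** The concern holds in limited form. Intention-to-treat is asserted but not delivered by the change t-tests and ANCOVA, because no week-3 score is sought or imputed for children who stop. It affects the trained-versus-waitlist comparisons of SSRS-P and BRIEF. It does not affect attendance, recruitment or completion, which need no week-3 score.

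The loss of 13 or 14 children follows from the plan's own attrition figure. The bias, from nil to about 0.31 SD with type I error from 5% to about 20%, rests on assumed loss splits and correlations and is illustrative only. The documents do not support the claim that the trial will be biased by any particular amount, or in a known direction. Because these are secondary outcomes in a trial sized on pilot guidance, this should be corrected, but it does not undermine the design.

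**What to change.** 1. Define the analysis set as all randomised children, analysed as allocated.
2. Seek the parent-rated SSRS-P and BRIEF at week 3 from every family, whatever the attendance, at the same time point in all three arms. This does most to close the gap, since Step 6 shows that analysis alone recovers little.
3. Reconcile the any-absence termination rule with the 9-of-12 completion rule, and say whether termination ends training only or also ends assessment.
4. For scores still missing, name the baseline-adjusted ANCOVA as the main efficacy analysis of these secondary outcomes, with multiple imputation if wanted. Do not rely on sessions attended as a predictor. It is constant in the waitlist arm, and under the any-absence rule nearly constant among trained children who have a week-3 score.
5. Add a sensitivity analysis that imputes missing trained children from the waitlist's change. Use multiple imputation, because a single mean understates the variance.
6. If week-3 scores are neither sought nor imputed, call the result complete-case.

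The cost is SAP wording, a few extra questionnaires, and estimates that may be slightly wider or less favourable.
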